5.6 APPENDIX 6 SELECTION CRITERIA FOR AE/MEDICATION GROUPINGS

Table 14 - List of PTs or Medications for CMQs/CDGs

Grouping	Preferred Term/Medication Code	Preferred Term/Medication
Conjunctivitis	10001257	Adenoviral conjunctivitis
Conjunctivitis	10010725	Conjunctival irritation
Conjunctivitis	10010726	Conjunctival oedema
Conjunctivitis	10010736	Conjunctival ulcer
Conjunctivitis	10010741	Conjunctivitis
Conjunctivitis	10010744	Conjunctivitis allergic
Conjunctivitis	10010745	Conjunctivitis chlamydial
Conjunctivitis	10010749	Conjunctivitis gonococcal neonatal
Conjunctivitis	10010754	Conjunctivitis tuberculous
Conjunctivitis	10010755	Conjunctivitis viral
Conjunctivitis	10018258	Giant papillary conjunctivitis

Grouping	Preferred Term/Medication Code	Preferred Term/Medication
Conjunctivitis	10021629	Inclusion conjunctivitis
Conjunctivitis	10030861	Ophthalmia neonatorum
Conjunctivitis	10048908	Seasonal allergy
Conjunctivitis	10049458	Herpes simplex virus conjunctivitis neonatal
Conjunctivitis	10051625	Conjunctival hyperaemia
Conjunctivitis	10053991	Inclusion conjunctivitis neonatal
Conjunctivitis	10061784	Conjunctivitis bacterial
Conjunctivitis	10062889	Pingueculitis
Conjunctivitis	10063669	Photoelectric conjunctivitis
Conjunctivitis	10067317	Oculorespiratory syndrome
Conjunctivitis	10067817	Acute haemorrhagic conjunctivitis
Conjunctivitis	10069166	Blebitis
Conjunctivitis	10071570	Ligneous conjunctivitis
Conjunctivitis	10074701	Noninfective conjunctivitis
Conjunctivitis	10075264	Oculoglandular syndrome
Conjunctivitis	10080825	Conjunctivitis fungal
Conjunctivitis	10084034	Conjunctival suffusion
Intravenous immunoglobulin therapy	CAS 8000012671	IMMUNOGLOBULIN HUMAN NORMAL
Intravenous immunoglobulin therapy	CAS 8000050682	IMMUNOGLOBULIN, PORCINE
Intravenous immunoglobulin therapy	CAS 8000056919	IMMUNOGLOBULIN G HUMAN
Intravenous immunoglobulin therapy	CAS 8600000563	IMMUNOGLOBULINS NOS
Intravenous immunoglobulin therapy	CAS 8600001670	IMMUNOGLOBULIN HUMAN NORMAL SLRA
Intravenous immunoglobulin therapy	CAS 8600001671	IMMUNOGLOBULIN HUMAN NORMAL IFAS
Intravenous immunoglobulin therapy	RECNO 900708	OTHER IMMUNOGLOBULINS
Intravenous immunoglobulin therapy	RECNO 900722	IMMUNE SERA AND IMMUNOGLOBULINS
Intravenous immunoglobulin therapy	RECNO 900728	IMMUNOGLOBULINS
Intravenous immunoglobulin therapy	RECNO 900914	SPECIFIC IMMUNOGLOBULINS
Intravenous immunoglobulin therapy	RECNO 901112	IMMUNOGLOBULINS, NORMAL HUMAN

Abbreviations: CAS : Chemical Abstract Service Registry Number RECNO : Drug Record Number

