8.3 ADVERSE EVENTS AND SERIOUS ADVERSE EVENTS

Adverse event of special interest

An AESI is an AE (serious or nonserious) of scientific and medical concern specific to the Sponsor's product or program, for which ongoing monitoring and immediate notification by the Investigator to the Sponsor is required. Such events may require further investigation in order to characterize and understand them. Adverse events of special interest may be added, modified or removed during a study by protocol amendment.

For these AESIs, the Sponsor will be informed immediately (ie, within 24 hours), per SAE notification described in [Section 10.3](#), even if not fulfilling a seriousness criterion, using the corresponding pages in the CRF (to be sent) or screens in the eCRF. If an SAE or any AESI of anaphylactic reactions or systemic allergic reactions that are related to IMP and require treatment, or severe injection site reactions lasting longer than 24 hours, occurs in a participant, blood samples should be collected for determination of functional dupilumab concentration, and ADA assessment at or near the onset and completion of the occurrence of the event, if possible.

- Anaphylactic reactions.
- Systemic hypersensitivity reactions.
- Helminthic infections.
- Any severe type of conjunctivitis or blepharitis.
- Keratitis.

- Clinically symptomatic eosinophilia (or eosinophilia associated with clinical symptoms).
- Pregnancy of a female subject entered in a study as well as pregnancy occurring in a female partner of a male subject entered in a study with IMP/NIMP;
 - Pregnancy occurring in a female participant entered in the clinical trial or in a female partner of a male participant entered in the clinical trial. It will be qualified as an SAE only if it fulfills one of the seriousness criteria,
 - In the event of pregnancy in a female participant, IMP should be discontinued,
 - Follow-up of the pregnancy in a female participant or in a female partner of a male participant is mandatory until the outcome has been determined,
 - Abnormal pregnancy outcomes (eg, spontaneous abortion, fetal death, stillbirth, congenital anomalies, ectopic pregnancy) are considered SAEs.
- Significant ALT elevation
 - ALT >5 x ULN in participants with baseline ALT ≤ 2 x ULN;
OR
 - ALT >8 x ULN if baseline ALT >2 x ULN.
- Symptomatic overdose (serious or nonserious) with IMP/NIMP

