Anaphylactic reaction	Anaphylactic reaction algorithmic approach (Introductory Guide for Standardised MedDRA Queries (SMQs) Version 18.1): includes anaphylactic reaction narrow SMQ (20000021) terms and programmatic identification of cases based on occurrence of at least two preferred terms meeting the algorithm criteria occurring within 24 hours of each other. The latter cases identified using the algorithm will undergo blinded medical review taking into account the timing of events relative to each other and to IMP administration for final determination of an anaphylactic reaction or not.
Systemic hypersensitivity reactions	SMQ [20000214] hypersensitivity narrow search and [AE corrective treatment/therapy='Y' or Action taken with IMP='Drug withdrawn' or Action taken with IMP='Drug interrupted'] followed by blinded medical review (documented process) for selection of relevant systemic hypersensitivity events
Helminthic infections	CMQ10544 based on HLGT as "Helminthic disorder"
Any severe type of conjunctivitis	CMQ10498 based on PTs (See Section 5.6) ^a and "Severe" ticked in Adverse Events eCRF page
Any severe type of blepharitis	CMQ10497 based on HLGT as "Lid, lash and lacrimal infections, irritations and inflammations" and "Severe" ticked in Adverse Events eCRF page
Keratitis	CMQ10642 based on the following PTs [keratitis, allergic keratitis, ulcerative keratitis, atopic keratoconjunctivitis, herpes ophthalmic, ophthalmic herpes simplex, corneal infection] ^a
Clinically symptomatic eosinophilia (or eosinophilia associated with clinical symptoms) ^b	CMQ10641 based on HLGT = Eosinophilic disorders or PT=Eosinophil count increased

AE Grouping	Criteria
Pregnancy of a female participants entered in a study as well as pregnancy occurring in a female partner of a male participant entered in a study with IMP/NIMP	“Pregnancy” or “Partner Pregnancy” checked on the Pregnancy eCRF page as reported by the investigator
Significant ALT elevation	“ALT increase” and AESI answer “Yes” checked on AE eCRF as reported by the investigator (ALT >5 x ULN in participants with baseline ALT ≤2 x ULN; OR ALT >8 x ULN if baseline ALT >2 x ULN)
Symptomatic overdose with IMP	Symptomatic Overdose is answered Yes, with Overdose of IMP answered Yes on AE eCRF.
Symptomatic overdose with NIMP	Symptomatic Overdose is answered Yes, with Overdose of NIMP answered Yes on AE eCRF.
Other selected AE Grouping	

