Serious injection site reactions or severe injection site reactions that last longer than 24 hours	HLT = ‘Injection site reaction’ and either with serious status, or with severe status and (AE end date/time - AE start date/time) ≥24 hours or ongoing
Severe or serious infection	Primary SOC = ‘Infections and infestations’ and with severe or serious status
Drug-related hepatic disorder	SMQ [20000006] Drug-related hepatic disorders- narrow
Injection site reaction	HLT = ‘Injection site reaction’
Malignancy	SMQ [20000091]- Malignant or unspecified tumors narrow
Suicidal behavior	CMQ10639 based on the following PTs [Completed suicide, Suicidal ideation, Depression suicidal, Suicidal behavior, Suicide attempt] ^a
Conjunctivitis (narrow)	CMQ10644 based on the following PTs [Conjunctivitis, Conjunctivitis allergic, Conjunctivitis bacterial, Conjunctivitis viral, Atopic keratoconjunctivitis] ^a
Conjunctivitis (broad)	CMQ10645 based on the following PTs [Conjunctivitis, Conjunctivitis allergic, Conjunctivitis bacterial, Conjunctivitis viral, Atopic keratoconjunctivitis, Blepharitis, Dry eye, Eye irritation, Eye pruritus, Lacrimation increased, Eye discharge, Foreign body sensation in eyes, Photophobia, Xerophthalmia, Ocular hyperaemia, Conjunctival hyperaemia] ^a
Conjunctivitis (FDA) ^c	CMQ10643 based on the following PTs [Conjunctivitis, Conjunctivitis allergic, Conjunctivitis bacterial, Conjunctivitis viral, Eye irritation, Eye inflammation, Giant papillary conjunctivitis] ^a
Keratitis (FDA) ^c	CMQ30102 based on the following PTs in (keratitis, ulcerative keratitis, allergic keratitis, atopic keratoconjunctivitis, and ophthalmic herpes simplex)

a The list of terms may be adjusted according to MedDRA version changes

b All cases of Eosinophilia will be included in the analysis, where cases associated with clinical symptoms will be further described in the CSR

c FDA requested for US labeling

The following summaries will be provided:

- All TEAEs, by selected standardized MedDRA query (SMQ)/Customized MedDRA query (CMQ) and PT or by laboratory values (as in alanine aminotransferase (ALT) elevation), showing the number (%) of participants with at least 1 PT,
- For each AESI and other selected AE groupings,
 - Number (%) of participants with any specific TEAE
 - Number (%) of participants with any specific serious AE (regardless of treatment emergent status)
 - Number (%) of participants with any specific treatment emergent serious AE

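### The term list behind the severe-conjunctivitis AESI row includes Seasonal allergy, so a severe allergic event with no eye involvement can be counted as severe conjunctivitis

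*SAP*

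**What the plan says.** Protocol Section 8.3 lists among the adverse events of special interest "Any severe type of conjunctivitis or blepharitis".

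SAP Section 4.7.2, Table 8, turns the conjunctivitis half into a row selected by "CMQ10498 based on PTs", with a pointer to Section 5.6 and the added condition that severe intensity is ticked on the adverse event page. Section 5.6, Table 14, holds the list. One entry, code 10048908, is "Seasonal allergy".

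Table 8 also defines three other conjunctivitis groupings:
- The narrow grouping is "Conjunctivitis, Conjunctivitis allergic, Conjunctivitis bacterial, Conjunctivitis viral, Atopic keratoconjunctivitis".
- The broad grouping starts from the same five terms and adds eleven eye signs and symptoms, such as dry eye and photophobia.
- The FDA grouping is "CMQ10643 based on the following PTs [Conjunctivitis, Conjunctivitis allergic, Conjunctivitis bacterial, Conjunctivitis viral, Eye irritation, Eye inflammation, Giant papillary conjunctivitis".

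In the same table, blinded medical review is written into the systemic hypersensitivity row and into the algorithm-identified anaphylaxis cases. None is written into the severe-conjunctivitis row. Footnote a provides for changes to the term lists only when the MedDRA version changes.

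**The concern.** A row labelled severe conjunctivitis should contain severe conjunctivitis. Seasonal allergy names an allergic condition that need not involve the eye. With term and intensity as the only conditions, and no reviewer to set a case aside, the programmed row takes in any severe event coded to that term.

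The row also feeds other outputs in Section 4.7.2. The overview of treatment-emergent events has a line for any AESI, and the exposure-adjusted incidence tables cover the AESIs in Table 8. A false count carries into both.

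The setting makes the term relevant. Protocol Section 2.3 names conjunctivitis among the identified adverse drug reactions, so readers will look at this row. Protocol Section 6.3 defines the atopic stratum to include allergic rhinitis and rhinoconjunctivitis, so people prone to seasonal allergy are enrolled on purpose. Rows restricted to severe events may hold few cases, and then a single false one could change how the row reads.

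**Working it through.** **Step 1. Compare the lists.** The source is SAP Table 8 for the three groupings and Table 14 for the AESI list.

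| List | Terms | Shared with Table 14 | Seasonal allergy | Atopic keratoconjunctivitis |
|---|---|---|---|---|
| Table 14 (AESI row) | 28 | – | yes | no |
| Narrow | 5 | 4 | no | yes |
| Broad | 16 | 5 | no | yes |
| FDA | 7 | 5 | no | no |

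Of the 28 Table 14 terms, 22 name the conjunctiva or conjunctivitis. The other six are Ophthalmia neonatorum, Pingueculitis, Oculorespiratory syndrome, Blebitis, Oculoglandular syndrome and Seasonal allergy. The first five refer to the eye; Seasonal allergy does not. The broad grouping is the one built to be inclusive, and it leaves the term out too. The SAP gives no reason for the difference.

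**Step 2. Follow one event through the rules.** A treatment-emergent event coded to Seasonal allergy and ticked severe meets both conditions of the row. No later step removes it. It adds one participant to the row if that participant has no other qualifying event, and one to the any-AESI line if that participant has no other AESI.

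**Step 3. Size of the atopic group.** Protocol Section 9.2 gives about 150 participants, 75 per arm, with each atopy group capped at 60%. Each group is therefore at least 100% − 60% = 40%. Atopic participants number 0.40 × 150 = 60 to 0.60 × 150 = 90.

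**Step 4. Chance of at least one false count.** The documents give no rate of severe seasonal allergy events, so an expected count cannot be derived from them. As an illustration only, assume a per-participant probability p and independence. The chance of at least one such event is 1 − (1 − p)^n.

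| Assumed p | n = 75 (one arm) | n = 150 (both arms) |
|---|---|---|
| 0.1% | 1 − 0.999^75 = 7% | 1 − 0.999^150 = 14% |
| 0.5% | 1 − 0.995^75 = 31% | 1 − 0.995^150 = 53% |
| 1% | 1 − 0.99^75 = 53% | 1 − 0.99^150 = 78% |

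**Step 5. Effect of one false count.** 1/75 = 1.3 percentage points in the arm where it falls.

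**Step 6. Effect of the change.** Removing Seasonal allergy leaves 28 − 1 = 27 terms. The row still shares four of the five narrow terms, because Atopic keratoconjunctivitis is a separate question.

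**The case against.** The strongest reply is that the plan already contains tables that would expose or bypass the problem. Section 4.7.2 plans summaries by query and preferred term, so a seasonal allergy case would appear on its own line under the conjunctivitis query. It plans each grouping by maximum intensity, so severe events in the narrow grouping are tabulated without Seasonal allergy. It also summarizes investigator-reported AESIs separately, and that summary does not use Table 14. Section 4.7 makes all safety analyses descriptive. This stands and limits the harm. It does not put the row right: the narrow grouping lacks 28 − 4 = 24 of the Table 14 terms and cannot replace it, and the any-AESI line and exposure-adjusted rates would still carry the false count.

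A second reply is that the query is a company standard and that editing it for one trial harms comparability across studies. That is a fair reason to leave the query alone. It is not a reason against reviewing the cases it selects.

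A reader might infer more than the documents support:
- That severe Atopic keratoconjunctivitis is lost. It is not. Table 8 counts it at any severity under the Keratitis AESI, and the FDA conjunctivitis list omits it as well. Its absence from Table 14 may be deliberate.
- That the blepharitis row is too wide in the same way. It uses the group "Lid, lash and lacrimal infections, irritations and inflammations", but the documents do not list that group's terms, so neither the excess nor a narrower list can be specified from them.
- That active treatment lowers seasonal allergy, so the false counts would hide a real excess. Nothing in the documents supports a difference between arms in this term.

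**Conclusion.** The specification error is real and narrow. As written, the severe-conjunctivitis AESI row can include events that are not conjunctivitis, through one term that no other conjunctivitis grouping in the SAP contains. It would be too strong to say that the row is miscounted: that requires a severe, treatment-emergent event coded to Seasonal allergy in someone with no other qualifying event.

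The frequency is unknown. The percentages in the working rest on assumed rates. The 60-90 atopic participants should not be read as people with seasonal allergy, because the stratum also covers atopic dermatitis, asthma and food allergy, and a history alone is enough.

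This is a minor point affecting one descriptive safety row and the two summaries that draw on it. Efficacy, type I error and power are untouched.

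**What to change.** Before the primary database lock, remove Seasonal allergy (10048908) from the selection for the severe-conjunctivitis AESI row and record the change in the SAP, since footnote a of Table 8 provides only for dictionary version changes. If the company query cannot be edited, keep it and add to this row the blinded medical review that Table 8 already uses for systemic hypersensitivity, so that an event coded to this term counts only after review.

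As a clarification only, add a sentence saying whether Atopic keratoconjunctivitis is meant to count under the Keratitis AESI alone or also in this row.

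The cost is a one-term edit or a short blinded review, and a footnote noting the difference from the company-standard query where results are pooled across studies.

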5.7 APPENDIX 7 MEDICATION/PROCEDURE ADJUDICATION ALGORITHM

Algorithm for determining whether treatment with following medications or procedures constitutes treatment failure resulting in setting data as non-responder after taking medication or undergoing procedure in the main statistical analysis

1. Not required to adjudicate post-baseline medications (WHODD-coded) or procedures (CMQ-coded) as these will be considered treatment failures if used at any time¹.
 - a) Always considered treatment failure
 - ATC2 = CORTICOSTEROIDS FOR SYSTEMIC USE
 - ATC2=IMMUNOSUPPRESSANTS (systemic, eg, oral or parenteral route)
 - Preferred Drug Name = Ciclosporin
 - Preferred Drug Name = Methotrexate
 - Preferred Drug Name = Mycophenolate sodium
 - Preferred Drug Name = Mycophenolic acid
 - Preferred Drug Name = Azathioprine
 - Preferred Drug Name = Gabapentin
 - Preferred Drug Name = Pregabalin
 - Preferred Drug Name = Thalidomide
 - Preferred Drug Name = Lenalidomide
 - Preferred Drug Name = Baricitinib
 - Preferred Drug Name = Ruxolitinib
 - Preferred Drug Name = Tofacitinib
 - Preferred Drug Name = AbrocitinibPreferred Drug Name = Delgocitinib
 - Preferred Drug Name = Nalbuphine
 - Preferred Drug Name = Naltrexone
 - Preferred Drug Name = Naloxone
 - Preferred Drug Name = Vixarelimab
 - Preferred Drug Name = Nemolizumab
 - Preferred Drug Name = Serlopitant
 - Preferred Drug Name = Aprepitant
 - CMQb HLT Phototherapies
 - CMQ Tanning_single PT
 - b) Never considered treatment failure:
 - ATC2 = EMOLLIENTS AND PROTECTIVES

- ATC2 = GENERAL NUTRIENTS
- ATC2 = VITAMINS
- ATC2 = ANTIVIRALS FOR SYSTEMIC USE
- ATC2 = ANTIFUNGALS FOR DERMATOLOGICAL USE
- ATC2 = ANTISEPTICS AND DISINFECTANTS
- ATC2 = ANTIBIOTICS AND CHEMOTHERAPEUTICS FOR DERMATOLOGICAL USE
- ATC2 = ANTI-ACNE PREPARATIONS, excluding D10AA Corticosteroids, combinations for treatment of acne
- ATC2 = OPHTHALMOLOGICALS
- ATC1 = ANTIINFECTIVES FOR SYSTEMIC USE, excluding D07C Corticosteroids, combinations with antibiotics
- ATC1 = BLOOD AND BLOOD FORMING ORGANS
- ATC1 = ALIMENTARY TRACT AND METABOLISM
- ATC1 = MUSCULO-SKELETAL SYSTEM, excluding M01BA Antiinflammatory/antirheumatic agents in combination with corticosteroids
- ATC2 = COUGH AND COLD PREPARATIONS
- ATC2 = PSYCHOLEPTICS, excluding N05BB Diphenylmethane derivatives and N05C HYPNOTICS AND SEDATIVES

¹ A blinded review of all post-baseline medications or procedures to adjudicate whether treatment constitutes treatment failure, based on medical judgment, may be performed in addition. A listing of treatments or procedures classified as treatment failure in a manner inconsistent with the classification under #1 will be provided, along with supporting rationale.

2. Require to adjudicate medications or procedures that may constitute treatment failure

- All other medications and procedures listed in the protocol and [Table 5](#) of the SAP (not noted in 1. above) given for indications consistent with PN²
- Considerations in determining treatment failure include the criteria already set forth in [Table 5](#) of the SAP in addition to the type of medication or procedure, indication, dose, route of administration, timing, frequency and the potential impact of the use of the prohibited medications/procedures and rescue medications on the primary and key secondary efficacy endpoints.

2 Below is a list of indications consistent with PN based on PT level from concomitant medication/procedure data using MedDRA dictionary

System Organ Class	High Level Term	Preferred Term	Preferred Term Code
Skin and subcutaneous tissue disorders	Dermatitis and eczema	Neurodermatitis	10029263
Infections and infestations	Bacterial infections NEC	Eczema impetiginous	10051890
Infections and infestations	Skin structures and soft tissue infections	Dermatitis infected	10012470
Infections and infestations	Skin structures and soft tissue infections	Eczema infected	10014199
Skin and subcutaneous tissue disorders	Dermatitis and eczema	Dermatitis	10012431
Skin and subcutaneous tissue disorders	Dermatitis and eczema	Dermatitis atopic	10012438
Skin and subcutaneous tissue disorders	Dermatitis and eczema	Eczema	10014184

Signature Page for VV-CLIN-0602722 v5.0
efc16459-16-1-9-sap

Approve & eSign

Approve & eSign

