6.5 CONCOMITANT THERAPY

Any medication or vaccine (including over-the-counter or prescription medicines, vitamins, and/or herbal supplements) that the participant is receiving at the time of enrollment or receives during the study must be recorded along with:

- Reason for use.
- Dates of administration including start and end dates.
- Dosage information including dose and frequency.

The concomitant use of non-sedating antihistamine administration is allowed during the study except for treatment of AD or PN, but dose change of non-sedating antihistamine is not allowed both from Week 11 to Week 12 and from Week 23 to Week 24.

The concomitant use of the following therapies is prohibited during the entire study. Study treatment will need to be discontinued in participants receiving these treatments:

- Systemic immunosuppressive/immunomodulating drugs (eg, systemic corticosteroids, cyclosporine, mycophenolate-mofetil, interferon gamma, Janus kinase inhibitors, azathioprine, methotrexate, hydroxychloroquine, dapsone, sulfasalazine, colchicine, etc).
- Other monoclonal antibodies (which are biological modifiers).
- Phototherapy, including tanning beds.
- Naltrexone or other opioid antagonist.
- Gabapentin, pregabalin, and thalidomide.

The concomitant use of the following therapies is prohibited except if the dose has been stable for at least 3 months prior to screening, but study treatment will not need to be discontinued in participants receiving the treatments listed below. The dose should also remain stable (can be reduced or discontinued if medically indicated), but should not be initiated or increased throughout the study.

- Paroxetine, fluvoxamine, or other SSRIs.
- SNRIs.
- Amitriptyline or other tricyclic or tetracyclic antidepressants.

The concomitant use of the following therapies is also prohibited during the entire study, but study treatment will not need to be discontinued in participants receiving the treatments listed below.

- Intralesional corticosteroid injections and cryotherapy.
- Sedating antihistamine.
- Non-sedating antihistamine used specifically for the treatment of itch secondary to AD or PN.

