4.3 PRIMARY ENDPOINT(S) ANALYSIS

4.3.1 Definition of endpoint(s)

The primary endpoint for this study is the proportion of participants with improvement (reduction) in worst-itch numeric rating scale (WI-NRS) by ≥ 4 from baseline to Week 24.

WI-NRS is a patient-reported outcome (PRO) comprised of a single item rated on a scale from 0 (“No itch”) to 10 (“Worst imaginable itch”). Participants are asked to rate the intensity of their worst pruritus (itch) over the past 24 hours using this scale.

The weekly average WI-NRS score at each week, which is defined as the average of daily non-missing scores within the week window of each week (see [Section 5.4](#)), will be used for analyses.

For efficacy analysis, [Table 5](#) presents the prohibited and rescue medications/procedures which will be considered as intercurrent events if the last column indicates as “Yes” and therefore be handled in the estimands for endpoints defined in [Table 3](#).

Table 5 - Prohibited medications/procedures and rescue medications that impact efficacy

Medication/procedure	Comment	Data to be set as non-responder after taking medication in the main statistical analysis (Yes/No) ^a /Selection criteria
Prohibited medications/procedures		
Systemic immunosuppressive/immunomodulating drugs (eg, systemic corticosteroids, cyclosporine, mycophenolate-mofetil, interferon gamma, Janus kinase inhibitors, azathioprine, methotrexate, hydroxychloroquine, dapsone, sulfasalazine, colchicine, etc)	IMP to be discontinued	Yes (CDG ^b Immunosuppressant drugs Narrow and SDG ^b Corticosteroids Narrow)
Other monoclonal antibodies (that are biological response modifiers).	IMP to be discontinued	Yes (SDG ^b SDGMonoclonal antibodies Narrow)
Phototherapy, including tanning beds.	IMP to be discontinued	Yes (CMQ ^b HLT Phototherapies, CMQ ^b Tanning_single PT)
Naltrexone or other opioid antagonist	IMP to be discontinued	Yes (SDG ^b Analgesia producing opioids NARROW)
Gabapentin, pregabalin, and thalidomide	IMP to be discontinued	Yes (CDG ^b Gabapentin mono and multi ingredients, Pregabalin mono and multi ingredients, or Thalidomide mono and multi ingredients)
Paroxetine, fluvoxamine or other SSRIs.	No IMP discontinuation, see requirement in the footnote	Yes ^{c,d} (CDG ^b N06AB selective serotonin reuptake inhibitors)
SNRIs.	No IMP discontinuation, see requirement in the footnote	Yes ^{c,d} (CDG ^b serotonin and norepinephrine reuptake inhibitors)

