Amitriptyline or other tricyclic or tetracyclic antidepressants	No IMP discontinuation, see requirement in the footnote	Yes ^{c,d} (CDG ^b N06AA non-selective monoamine reuptake inhibitors)
Intralesional corticosteroid injections and cryotherapy.	No IMP discontinuation	Yes ^d (CMQ ^b Injection_single pt, cryotherapy or skin cryotherapy PT)
Sedating antihistamine	No IMP discontinuation	Yes ^{d,e} (CDG ^b sedating antihistamines)
Non-sedating antihistamine if used specifically for the treatment of itch secondary to AD or PN	No IMP discontinuation	Yes ^{d,e} (CDG ^b non-sedating antihistamines)

Medication/procedure	Comment	Data to be set as non-responder after taking medication in the main statistical analysis (Yes/No) ^a /Selection criteria
Rescue medications		
Dermatological preparations of high potency or superpotent TCS and TCI	No IMP discontinuation	Yes ^d (CDG ^b calcineurin inhibitors and corticosteroids narrow, Ticked 'RESCUE THERAPY' in CRF page)
a When yes, the estimand for the intercurrent event handling strategy will be as follows: hypothetical for continuous endpoints, and composite for responder and time-to-event endpoints. When no, a treatment policy strategy will be applied. b CDG=company drug groupings, CMQ=company MedDRA query, SDG= Standardized drug groupings. c Only if the antidepressant is initiated during the study or its dose is increased from baseline provided that medication was taken at least 3 months prior to screening. d As per medical adjudication, see Section 5.7 for details. e Only if the medication is initiated at Week 12 or Week 24, or the dose is increased from Week 11 to Week 12 or from Week 23 to Week 24.		

Blinded review of prohibited/rescue treatment (medication or procedure) based on [Table 5](#) and a pre-specified algorithm ([Section 5.7](#)) will be implemented before database locks by considering the type of medication or procedure, indication, timing, frequency and the potential impact of the use of the prohibited medications/procedures and rescue medications.

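### SAP 5.7 ties required adjudication to seven skin terms without pruritus, which does not match Table 5 for one antihistamine row and, in part, for three unconditional rows

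*SAP*

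**What the plan says.** **Table 5 route.** SAP Table 3 makes a participant who takes a prohibited or rescue treatment before Week 24 a non-responder, and its footnote b identifies those treatments by Table 5. SAP 4.3.2 refers to Table 5 in the same way. SAP 4.3.1 treats a row as an intercurrent event if its last column is 'Yes', and all 12 rows are.

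**Referral to 5.7.** Seven rows carry footnote d: "As per medical adjudication, see Section 5.7 for details". One of them is "Non-sedating antihistamine if used specifically for the treatment of itch secondary to AD or PN". Protocol 6.5 uses almost the same wording: "Non-sedating antihistamine used specifically for the treatment of itch secondary to AD or PN". The other five rows carry no footnote d.

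**SAP 5.7.** Item 1a lists treatments that always count as failure, and item 1b lists classes that never do. Item 2 requires adjudication of the remaining treatments in the protocol and Table 5 "given for indications consistent with PN". Footnote 2 defines that phrase: "Below is a list of indications consistent with PN based on PT level from concomitant medication/procedure data using MedDRA dictionary". The terms shown are Neurodermatitis, Eczema impetiginous, Dermatitis infected, Eczema infected, Dermatitis, Dermatitis atopic and Eczema.

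**The concern.** The filter in item 2 leaves out itch, although itch is the primary endpoint and defines one of the rows sent to 5.7. It also reaches treatments for which Table 5 sets no indication condition. As written, the same drug can enter or miss required adjudication depending on whether the site recorded itch or eczema as the reason for use.

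The classification sets non-responder status for the primary endpoint. It does the same for the key secondary endpoints, which use the same estimand (SAP 4.4.1.2), and it triggers worst-observation imputation for continuous endpoints (SAP 4.4.2). If the two texts are reconciled only after unblinding, the choice will be open to challenge as data-driven.

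**Working it through.** The plan states no figure to reproduce here. The check sets Table 5 beside 5.7.

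**1. Row count.** Table 5 has 11 prohibited rows and 1 rescue row, 12 in all. Footnote d is on 7: SSRIs, SNRIs, tricyclic/tetracyclic antidepressants, intralesional steroid or cryotherapy, sedating antihistamine, non-sedating antihistamine, and rescue TCS/TCI. That leaves 12 − 7 = 5 without it.

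**2. Rows with footnote d.** Six of the seven simply defer to 5.7. There the filter narrows what must be adjudicated but contradicts nothing. The non-sedating antihistamine row differs because its own definition is itch secondary to AD or PN. Of the 7 listed terms, 0 are pruritus terms and none is named prurigo. Use coded to itch alone is therefore outside required adjudication.

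**3. Rows without footnote d, against item 1a.**

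| Table 5 row | What item 1a contains | Left over |
|---|---|---|
| Phototherapy, tanning | Both | Nothing |
| Gabapentin, pregabalin, thalidomide | All three | Nothing |
| Other monoclonal antibodies | Vixarelimab and nemolizumab; no antibody class line | Other antibodies, unless a class line captures them |
| "Naltrexone or other opioid antagonist" | Naltrexone, naloxone, nalbuphine | Other antagonists |
| Systemic immunosuppressive/immunomodulating drugs | Two class lines and individual names | See step 4 |

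**4. The systemic row.** Table 5 gives 11 examples, the last six being "azathioprine, methotrexate, hydroxychloroquine, dapsone, sulfasalazine, colchicine, etc" and the five before them systemic corticosteroids, cyclosporine, mycophenolate-mofetil, interferon gamma and Janus kinase inhibitors. (The closing 'etc' is not counted, so the last group is azathioprine, methotrexate, hydroxychloroquine, dapsone, sulfasalazine and colchicine.) Item 1a has systemic corticosteroids as a class, ciclosporin, azathioprine, methotrexate, and five named Janus kinase inhibitors. Counting that class as covered gives 5 of 11. By literal name 11 − 5 = 6 are absent: mycophenolate-mofetil (item 1a names the sodium salt and the acid), interferon gamma, hydroxychloroquine, dapsone, sulfasalazine and colchicine. The count is at least 6, because the Janus kinase class appears only as five products. The class line for systemic immunosuppressants may capture some of the six; its content is not in the documents.

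**5. Outcome for a product in these three rows that no item 1 line covers.** Table 5 says 'Yes', whatever the indication. Under 5.7 the product is adjudicated if given for one of the seven terms, and 5.7 states no outcome otherwise. No text says which governs.

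**6. Size.** With 75 planned per arm, one participant whose responder status changes moves that arm's response rate by 1/75 = 0.0133, or 1.33 percentage points. A misclassified participant who is a non-responder anyway moves nothing.

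**The case against.** A reader might infer that the plan leaves these treatments with no route to classification. The documents do not support that. Table 3 footnote b, 4.3.1 and 4.3.2 classify directly from Table 5. Table 5 gives drug groupings for the rows in question and calls on 5.7 only through footnote d. The natural reading for rows without footnote d is that Table 5 decides. What is missing is a sentence saying so, because item 2 claims every Table 5 treatment not noted in item 1.

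A reader might also infer that only the seven terms can ever lead to adjudication. Item 2 says what must be adjudicated; it forbids nothing further, and the SAP does not call the list exhaustive, though it has no open-ended wording either. Three reviews help in part:

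- Footnote 1 of 5.7 allows a blinded review of all post-baseline medications and procedures, but it is optional and attached to item 1.
- The blinded review described after Table 5 will take place, but it rests on both Table 5 and 5.7 and so inherits the mismatch.
- The review of all medications in Protocol 6.5.1 and SAP 5.3 is mandatory, but its purpose is to adjudicate rescue.

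It is also fair to say that the itch gap is narrow. Dermatitis atopic is listed, and prurigo may code to a listed term. An entry of itch alone does not prove that the itch is secondary to AD or PN. Footnote e limits the row to initiation at Week 12 or 24, or a dose increase from Week 11 to 12 or Week 23 to 24. All of this stands. It shrinks the problem and does not remove it.

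**Conclusion.** The point holds in limited form. Item 2's indication filter does not match Table 5 for non-sedating antihistamine use coded to itch alone, which is a narrow gap. It also does not match for products in three unconditional rows that no item 1 line covers, where two texts apply and neither is given precedence. This should be corrected, but it does not undermine the primary analysis as a whole.

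Frequency and direction cannot be derived from the documents. An inference that the rule favours one arm is unsupported, and the review is blinded. The only fixed figure is 1.33 points per participant whose responder status actually changes. The as-observed supplementary analysis (SAP 4.3.4) uses data after prohibited and rescue treatment, so it does not depend on this classification and will show how far the results do.

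The conclusion assumes that the seven terms shown are the full list. It also rests on dictionary content that the documents do not give: the members of the item 1 classes and the terms to which itch and prurigo were coded.

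**What to change.** Under blind and before database lock:

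1. Add to footnote 2 of SAP 5.7 the preferred terms to which itch/pruritus and prurigo indications code in this database.
2. Add one precedence sentence to 5.7: Table 5 rows marked 'Yes' without footnote d are classified by Table 5 whatever the indication, as 4.3.1 and 4.3.2 already read. If the sponsor instead intends an indication condition for those rows, Table 5 must carry it.
3. Check that no treatment in those rows codes to an item 1b class, which would count it as never a failure.

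The cost is a few terms and one sentence in an appendix, one coding check, and a slightly longer blinded review by people already doing it. Sample size, alpha and data collection are unaffected.
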